## 5 Data Analysis

Describe the data analysis plan, including any statistical procedures or power analysis.

The data will be randomly assigned with serial ID numbers. All tests will be assumed two-sided and an alpha level of .05 will be used. SAS 9.4 will be used for data processing and all statistical analyses. Missing data will be handled by multiple imputations of dependent values. 101–103 Analyses just of complete data will be conducted and comparisons of groups with and without missing data will be made. In addition, sensitivity analyses of complete data will be conducted and compared imputed data analysis. An **intent-to-treat** analysis will be employed. For **Hypotheses 1 to 3**, differences in continuous outcome measures over time will be examined using **linear mixed-effects modeling.** In particular, we will fit mixed effects models to each continuous outcome measure. We will use random intercepts as well as explore random slopes to represent subject level variability. Fixed-effects corresponding to group, time and group x time interaction will be included in the model. A significant group x time interaction will indicate substantial differences in the groups over time. Restricted maximum likelihood method will be used for estimation, and the most appropriate covariance structure will be examined.

Since Data and Safety Monitoring Boards (DSMBs) are required only for phase III clinical trials (NOT-OD-00-038.html), we do not include a DSMB for this intervention study. For the proposed intervention study, we have

the following data safety monitoring plan (DSMP). First, to manage and protect the data collected, only summary data will be openly accessible to funding agency or will appear in publications. Research participants will be informed that they are free to decline to answer any questions they do not wish to answer or to stop participating in the project at any time. When a participant withdraws from participation, the data that they have provided will be immediately removed. Also, the data will have no identifying information to link a subject to the data.

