#### Phase 2 (Aim 2)

All research activities in Phase 2 will be done virtually. The study website will be developed first. The study website is the Web-App of the intervention program. The website at Emory was originally developed and refined by the other PI, [name], and it is owned by [name]. As soon as the grant transfer is completed, the website will be housed at The Univ. of Texas at Austin. To access/use the program through the website, the participants will be provided with an account with ID and passwords, which they could change at their convenience. The data collected through the website will be just the data on the participants' activities in the website (e.g., how many times per week they log in and out, what components they used in the website, how many messages that they are posting) that will be used to determine the dose-response effect of the program later. The current website at Emory is: https://tacad.nursing.emory.edu Again, the website will be moved to UT- Austin once the grant transfer is completed, which requires this IRB approval.

When potential participants visit the website, they will review the "informed consent" and click "I agree to participate" if they agree. After checking them against the inclusion criteria, only those who meet the criteria will be automatically **randomized** into two groups within each sub-ethnic group using an automated random number generator through the website. The randomization will be done within each sub-ethnic group to have an adequate number of participants in each sub-ethnic group. The intervention group (Group 1) will use both TACAD and Alzheimer's Association (AA) website while the control group (Group 2) will use only AA website. The women will be asked to fill out the baseline questionnaire. Then, they will be provided with IDs and passwords to log on the website. Both groups will have an electronic instruction sheet on when they need to come back and fill out questionnaires (see the below for the instruments) and/or use TACAD (see the below for more information on TACAD). Also, both groups will use the AA website (see the below for more information on the website) for 3 months. Only the intervention group will use TACAD for 3 months. Basically, they need to use TACAD and/or the AA website whenever they want to use; no requirement for reimbursement. They are recommended to visit the

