## 17 Identification and/or Screening Procedures

Describe the identification and/or screening procedures below.

When potential participants visit the project website after seeing the study announcements posted on online and offline communities/groups, they will be provided with the information sheet (consent form) and asked to give their consent by clicking the "I agree to participate" button. Then, when they agree, they will be verified against the inclusion and exclusion criteria (see the above) by server-side programs. When they meet the criteria, they will be asked about their sub-ethnicity. Then, the potential participants will be divided into Chinese and Korean, and randomized into two groups using an automated random number generator via the project website.

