## **21** Consent and Assent Processes

Provide a detailed description of consent/assent procedures in the box below. Include: who will obtain consent, where will consent be obtained, how is consent obtained, how consent/assent is documented, and when the

consent process will occur in such a manner that participants will have sufficient time for adequate consideration.

NOTE: Upload copies of all consent/assent/permission forms/scripts to UTRMS-IRB in the "Consent Forms" section. This is required for UTRMS-IRB to appropriately stamp consent forms for approval.

When potential participants visit the project Web site, they will be asked to review the informed consent form that provides general information on the proposed project, including: (a) the purpose of the study, (b) staff on the study, (c) the data collection period, (d) potential physical and psychological risks involving inconvenience, confidentiality, and invasion of privacy, (e) their rights to withdraw, (f) how to maintain complete confidentiality (using IDs and passwords), (g) what they are being asked to contribute to the study, and (h) how their participation will be reimbursed. They will be asked to give their consent to participate by clicking I agree to participate. When the button is clicked, participants' profiles will be checked against the inclusion and exclusion criteria. Internet protocol addresses of the participants will also be monitored to detect multiple submissions by the same person. After getting the consent, the participants will be linked to the Qualtrics system to go through the screening process and fill out the pre-test questionnaire.

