## **35** Early Withdrawal

Only complete this section if there are planned conditions under which a participant will be withdrawn from the study. If not applicable, skip to next section. Include this information in your consent form.

A List the criteria for withdrawing individual participants from the study (e.g., safety or toxicity concerns, emotional distress, inability to comply with the protocol, or requirements from study sponsor).

To input text, click in the light grey area below.

While the participants fill out the questionnaire, several random questions that they have already answered will be repeated to check consistency for the purpose of **identity and authenticity verification**. When inconsistency is detected, the participant will not be allowed to continue her participation in the study. This mechanism has been used in the former studies of the PIs without a problem.

The participants have the right to leave a study at any time without penalty. If they want to withdraw, they need to send an email notification or a text message indicating their withdrawal to the research team. Participation is voluntary, refusal to participate will involve no penalty or loss of benefits to which the subject is otherwise entitled, and the subject may discontinue participation at any time without penalty or loss of benefits to which the subject is otherwise

entitled. New findings developed during the course of the research that may affect the subject's willingness to continue to participate will be provided to the subject.

B Describe any necessary procedures for ensuring the safety of a participant who has withdrawn early.

To input text, click in the light grey area below.

Those who withdraw will be encouraged to seek mental health help if and when necessary, but no further actions from the research team after they withdraw.

Describe any pre-specified criteria for stopping or changing the study protocol due to safety concerns.

To input text, click in the light grey area below.

None specific for this study. The study will follow the NIH policies and regulations.

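### Immediate removal of withdrawn women's data conflicts with the promised intent-to-treat analysis, and the order of baseline and randomisation is left unclear

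*Combined protocol and SAP*

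**What the plan says.** **Analysis and withdrawal.** Section 5 (Data Analysis) names an intent-to-treat analysis without defining the set. It also says "Missing data will be handled by multiple imputations of dependent values", and plans complete-data analyses and a comparison of women with and without missing data. The same section, and again section 38 (Privacy), has a withdrawing woman's data removed at once. Section 35 (Early Withdrawal) makes withdrawal a formal act, notified by email or text message. The proration schedule in section 45 (Compensation) provides for withdrawals after the pre-test and after the 1-month test.

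**Order of steps.** The Phase 2 (Aim 2) narrative says "After checking them against the inclusion criteria, only those who meet the criteria will be automatically" randomised within sub-ethnic group. It then describes the two groups, and next says "The women will be asked to fill out the baseline questionnaire". It continues: "Then, they will be provided with IDs and passwords to log on the website". Section 17 also goes from eligibility and sub-ethnicity to women being "randomized into two groups using an automated random number generator via the project website", and does not mention baseline. Section 21 says "profiles will be checked against the inclusion and exclusion criteria" when the consent button is clicked, and that afterwards "the participants will be linked to the Qualtrics system to go through the screening process and fill out the pre-test questionnaire". It does not place randomisation.

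**Consistency check.** Section 35 repeats some questions while a woman answers the questionnaire. "When inconsistency is detected, the participant will not be allowed to continue her participation in the study". The Instruments paragraph uses the same questionnaire at all three time points, except that sociodemographic and caregiving-history items are asked only at the pre-test.

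**The concern.** Intent-to-treat means that every randomised woman is analysed in her assigned arm with the data she gave. A rule that erases the record of anyone who withdraws makes this impossible for those women, and nothing in the plan reconciles the two statements. Withdrawals come after the start of an open intervention that only one arm receives, with coaching, so women may know their arm when they leave. If their reasons differ by arm, the remaining groups are no longer the randomised ones, and the record that would let a reader examine this is gone.

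The step order adds a second, smaller route out of the randomised groups. All three hypotheses in section 2 concern change from baseline and adjust for background factors. A woman randomised before baseline who never completes it has neither her baseline scores nor those covariates. Imputing dependent values might reach the scores but not the covariates. The plan has no rule for women barred by the consistency check.

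**Working it through.** **1. The plan's own figure.** Section 15 states 105 per group for a difference of 0.5, 80% power and type I error 0.00625. With SD = 1 (assumed; not stated) and a two-sided test, n = 2(2.734 + 0.842)² / 0.5² = 102.3, so 103 per group by the normal approximation; the exact t-test gives 105. The figure reproduces. The trial will enrol 60 (30 per group), and this point does not depend on the 105.

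**2. Intent-to-treat against removal.** Take a woman who completes the pre-test and the 1-month questionnaire and then notifies the team that she withdraws.

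- Under intent-to-treat she stays in her arm. Her two observed time points enter the mixed model, and the 3-month score is missing and can be imputed from them.
- Under sections 5 and 38 her questionnaires are gone. At most her allocation remains, since the website generated it.
- The mixed model and the imputation need her observed scores to account for why the later one is missing. Without them, the analysis is sound only if withdrawal is unrelated to outcome.
- She also cannot appear in section 5's own comparison of women with and without missing data.

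The ways out of the study are not treated alike:

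| Route | Data under the plan | Handling in analysis |
|---|---|---|
| Formal withdrawal (section 35) | Removed at once (sections 5, 38) | Cannot be as randomised with her data |
| Stops responding without notice | Removal rule need not apply | Mixed model and imputation can use them |
| Fails consistency check (section 35) | Participation stops; removal not stated | Not stated |
| Dismissed after PHQ-9 (Phase 2 narrative, section 32) | Not stated | Not stated |
| Abandons baseline after allocation | Baseline-only covariates missing | Not stated |

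**3. Order of steps.** Procedure Description asks for procedures in sequence. The Phase 2 narrative gives eligibility, randomisation, baseline, log-in details. Section 17 gives eligibility, sub-ethnicity, randomisation. Section 21 gives consent, screening, pre-test, and is silent on randomisation. No section puts baseline first, and none says outright that it is completed after allocation.

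**4. Size of the baseline issue (illustration).** The documents give no loss rate, so 5, 10 and 15% of 60 are assumed: 3, 6 and 9 women. A further assumption is that 60 counts women randomised, without replacement. The method is a two-sample t-test with two-sided alpha .05 and noncentrality δ·√(n₁n₂/(n₁+n₂)), δ in SD units. It is an approximation, not the planned mixed model.

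| Loss | Analysed | Detectable at 80% power | Power for 0.5 SD |
|---|---|---|---|
| 0% | 30/30 | 0.736 SD | 47.8% |
| 5% | 29/28 | 0.756 SD | 45.8% |
| 10% | 27/27 | 0.777 SD | 43.8% |
| 15% | 26/25 | 0.801 SD | 41.7% |

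The largest change is 0.801 − 0.736 = 0.065 SD. This table does not measure the removal conflict, for which the documents give no withdrawal rate.

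**The case against.** The case against is strongest on step order. In the Phase 2 narrative the baseline sentence comes after a description of the groups and carries no time word; only the next sentence begins with one. Section 21 puts screening and the pre-test in one flow, and screening must precede randomisation, so that flow fits baseline-first. This stands: the supported claim is that the order is unclear and, as narrated, unfavourable. A reader might infer that the sections contradict each other, or that women see their group before answering baseline. The documents show neither. Section 21 does not mention randomisation, and log-in details come after baseline, which makes early display of allocation less likely without ruling it out.

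Other points also hold. Sections 14 and 15 do not say that 60 counts randomised women; if recruitment runs until 60 have baseline data, the precision loss in the table disappears. The gift certificate for the pre-test works against abandoning it. The consistency check serves identity and authenticity verification, so some barred records may not be genuine participants. Intent-to-treat has an ordinary meaning, and the lack of a formal definition in a 60-woman pilot is missing detail more than error.

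None of this answers the removal rule. The ordinary meaning of intent-to-treat is what that rule prevents.

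**Conclusion.** The main point holds and should be fixed. Carried out as written, the plan removes formally withdrawn women from an analysis that it calls intent-to-treat. This rests on the text alone and remains even if baseline turns out to precede randomisation. Its size cannot be computed, because no withdrawal rate is given.

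Two stronger readings go too far. One is that all drop-outs are deleted: the rule concerns withdrawal, which section 35 ties to a notification, so silent drop-outs need not be affected. The other is that the result will be biased by arm: women may know their arm when they leave, so this is possible, but nothing in the documents shows it.

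The step order is secondary. On the narrated order, women can be lost at baseline after randomisation. Under an assumed 5 to 15% loss without replacement, the detectable difference rises by 0.02 to 0.065 SD from 0.736 SD, which is modest in a pilot already this small.

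**What to change.** **Withdrawal.** Choose one route and word sections 5 and 38 alike.

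- Keep data collected before withdrawal and define the intent-to-treat set as all women randomised, in their assigned arm. This needs a protocol modification and a changed statement to participants.
- Or keep the promise of removal, stop calling the analysis intent-to-treat, and report the number removed by arm. This leaves the promise unchanged, but the comparison is no longer of all women randomised.

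**Sequence.** State one order in the Phase 2 narrative and sections 17 and 21: consent, eligibility, completed baseline with consistency check, randomisation, display of allocation. Say that 60 counts women randomised at that point. If the website already works this way, a clarifying sentence is enough; otherwise its order must change. A few more women must be consented to randomise 60: 60/0.95 = 63.2, so 64; 60/0.90 = 66.7, so 67; 60/0.85 = 70.6, so 71, at the assumed losses.

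**Barred and dismissed women.** State that women stopped by a later consistency check, or dismissed under the Phase 2 narrative and section 32, stay in their randomised arm with the data they gave. Add a sensitivity analysis excluding records judged inauthentic. This concerns analysis only and leaves the dismissal rule as it is. It costs a few sentences and one extra analysis.

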months. Only the intervention group will use TACAD for **3 months**. Basically, they need to use TACAD and/or the AA website whenever they want to use; no requirement for reimbursement. They are recommended to visit the project website at least once a week and the intervention group is recommended to have weekly coaching/support sessions with the interventionists through chatting. At first time of use, the participants will have an informational session on the proper use of AA website and TACAD (with instructions on headsets) by phone and/or a webcam. During the intervention, the participants will provide their feedback on the research process as well as TACAD. Two weeks before the end of the 1st and the 3rd months, both groups will fill out the next set of the instruments; it usually takes about 30 minutes to complete each questionnaire. The questionnaires will be provided via **Qualtrics**. In addition, during the intervention period, the participants will be screened using the PHQ-9 only if the research team identifies severe depressive symptoms or suicidal ideation at any time point. We will make immediate recommendations for psychiatric referral for those with scores more than 10 on the PHQ-9 (the cut-point of moderate depressive symptoms; range=0~27) as the literature suggestsIn such cases, participants will also be dismissed from the study.

TACAD. TACAD has four components in three languages (English, Mandarin Chinese, and Korean): (a) 2 sub-ethnic specific social media sites; (b) interactive online educational modules; (c) online resources; and (d) a 360 degree video clipping (a replacement of the VR component that was originally planned). The original VR that we planned to use was discontinued by the developer and only a 360 degree video clipping of the VR component is currently available. Thus, the VR component was replaced with the 360 degree video clipping of the VR. Two languages other than English were adopted because they are the primary languages of Chinese Americans or Korean Americans. The comparability of different language versions has been ensured through the standard-back

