translation process. The social media sites will be assisted, coached/moderated, and monitored by culturally matched bilingual RNs under the supervision by PIs. Coaching/support through social mediate sites (with chat functions) will focus on: (a) changing attitudes toward and beliefs about AD and caregiving, (b) building selfefficacy for caregiving, (c) minimizing information needs and uncertainty, and (d) enhancing social support through multiple ways. Within the project website, a social media site (like Facebook) is included. The site is developed by [name] and owned by him. The participants' activities are daily monitored by the interventionists and [name] to prevent any possible harmful effects. The RNs will be trained by the PI. Her/his first 10 messages through social media sites and chat functions will be monitored/evaluated by the research team, and the team's feedback will be incorporated into her/his subsequent interactions. The social media site will be very similar to Facebook. All participants can post their messages (e.g., sharing their experience) and pictures and they can see others' postings. The participants will use their pseudonyms that they choose when they join the study, but their profile pictures will not be posted. All postings will be visible only at the project website. No identifiers will be used except pseudonyms. We also developed online educational modules while considering the women's cultural attitudes found in the literature: TACAD aims to correct misinformation on AD and caregiving by providing stateof-science evidence-based educational content and to provide examples of culturally appropriate caregiving strategies that can be easily adopted. Culturally relevant content (e.g., filial piety, respect for elderly, mind-body interactions, etc.) and culturally tailored educational materials and online resources from Asian scientific authorities are also incorporated. Again, 360 degree video clipping components based on "A Walk Through Dementia (WTD)" will be used to help caregivers learn more about the challenges their loved ones with dementia face, and to build empathy among the caregivers (subsequently changing their attitudes). WTD uses VR technology to give an idea of the challenges faced by people with dementia. Using 3 everyday scenarios (at the supermarket, on the road and at home), users are given insight into some of the symptoms that people with different forms of dementia including AD may experience. The original VR that we planned to use was discontinued by the developer and only 360 degree video clippings of the VR component is currently available. Thus, the VR component was replaced with the 360 degree video clippings of the VR. The 360 degree video clippings basically have the same content of the VR component without the 3-dimentionality, which could be just viewed through Youtube site without any device. They are:

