For instance, the webpage on caregiving includes information on caregiving, care option, financial/legal planning, caregiver health, daily care, stages and behaviors, and safety. The content will be available in the three languages at the project website. The usages of the AA website and additional information searches (the participants will use them only through the project website) will be automatically recorded through the project server and later used for data analyses. Both groups will be asked to maintain their usual care. The interventionists will weekly remind the control group to use the AA website.

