of healthcare so that the research team can refer them if an adverse event is identified during the data collection process. If participants do not have a regular source of healthcare, then the researcher will provide a list of nearby clinics or healthcare centers so they can go to for emergency healthcare, if needed. During the data collection process, online records of the intervention process will be monitored daily by the engineering PI, [name], to ensure data safety and security. Also, the records will be monitored daily by the interventionists who are RNs in consultation with a MD ([name]) and a NP ([name]), and any potential and actual medical risks and adverse reactions (e.g., severe depressive symptoms or suicidal ideation, etc.) will be identified. For effective communication during emergency situations, the research team will establish emergency communication channels before starting the study. In addition, during the intervention period, the participants will be screened using the PHQ-9 only if the research team identifies severe depressive symptoms or suicidal ideation. We will make immediate recommendations for psychiatric referral for those with scores more than 10 on the PHQ-9 (the cut-point of moderate depressive symptoms; range=0~27) as the literature suggests 107-110 In such cases, participants will also be dismissed from the study. Participants in both intervention and control groups will be encouraged to seek mental health help if and when necessary. Also, we will provide the participants with local mental health referrals and contact information for the National Suicide Prevention Lifeline (NSPI; [name]) or the crisis text line. If a participant is in imminent danger to self or others (at any time during the study), a proper authority (local police or dial 911) will be notified to ensure the individual's safety. Also, a participant's family may be notified with the participant's permission. Family members will be offered the fact sheet developed by the National Institute of Mental Health (NIMH), 111 and RN interventionists will help them learn about the signs and symptoms, risk factors, and warning signs of suicide.

All communication/reminder templates will be uploaded via Modification prior to administration.

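### Dismissing women with a PHQ-9 above 10 stops collection of a primary outcome in a symptom-dependent way, and could favour TACAD if staff notice distress more often in that arm

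*Combined protocol and SAP*

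**What the plan says.** **The rule.** Under Phase 2 (Aim 2), "the participants will be screened using the PHQ-9 only if the research team identifies severe depressive symptoms or suicidal ideation at any time point". A score above 10 leads to immediate referral, and then: "In such cases, participants will also be dismissed from the study". Section 32 repeats the rule. Neither place, nor Section 35 on early withdrawal, arranges for dismissed women to complete the questionnaires at 1 month (T1) or 3 months (T2). The inclusion and exclusion criteria do not screen out depression at entry.

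**How distress is noticed.** Section 32 says that "online records of the intervention process will be monitored daily", and that through review of the records by the nurse interventionists "any potential and actual medical risks and adverse reactions (e.g., severe depressive symptoms or suicidal ideation, etc.) will be identified". Sections 32 and 34 extend daily monitoring to all online interactions, and both arms complete the same instruments at all three time points.

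**Contact by arm.** In the TACAD arm, "the intervention group is recommended to have weekly coaching/support sessions with the interventionists through chatting". TACAD also includes a social media site, of which the plan says: "The participants' activities are daily monitored by the interventionists". TACAD women use both TACAD and the Alzheimer's Association (AA) website, "while the control group (Group 2) will use only AA website". For that arm the stated staff contact during follow-up is a reminder: "The interventionists will weekly remind the control group to use the AA website".

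**Analysis.** The Instruments paragraph makes the Women's Symptom Index, which covers physical and psychological symptoms, a primary outcome. Section 5 declares intent-to-treat, multiple imputation of dependent values, a complete-data analysis, and a comparison of women with and without missing data. It does not mention PHQ-9 dismissal.

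**The concern.** The rule ends measurement because of something close to the outcome being measured. Section 5 asks for every randomised woman to be analysed, yet a stated procedure stops collection of the scores that this needs.

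Whether the loss biases the arm comparison depends on whether it is balanced. The PHQ-9 is not scheduled, so dismissal requires both that a woman is distressed and that someone notices. TACAD gives women more occasions to write to staff and peers. If that leads to more dismissals in the TACAD arm, more of its most symptomatic women go unmeasured, and the arm can look better at T2 with no true benefit.

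Imputation helps to the extent that earlier scores predict the missing ones. Distress that arises between questionnaires is not in those scores. PHQ-9 values exist only for flagged women, and women above 10 have no later outcome from which the relation could be learned. Aim 2 estimates preliminary efficacy with 30 women per arm, so a few dismissals carry weight.

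**Working it through.** **Scale.** Section 15 gives 105 per group for 80% power, a type I error of 0.00625 and a difference of 0.5. With SD 1 and a two-sided test, n = 2(z₁₋α/₂ + z₀.₈)²/0.5² = 8 × (2.734 + 0.842)² ≈ 102.3, so 103. The t-test at 105 per group has power 80.4%. This agrees with the plan's figure and supports reading 0.5 in SD units.

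**Hand check.** Each extra dismissed TACAD woman shifts the arm difference by gap/30, where gap is how much worse her unseen score is than her imputed one. Assume 5 TACAD and 1 control dismissals and a gap of 1 SD: (5 − 1)/30 × 1 = 0.13 SD, and 0.133/0.5 = 27% of the planning difference.

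**Simulation with no true effect.** All rates and correlations here are assumptions; the documents give none. Scores have SD 1. Baseline correlates 0.5 with later values. T1, T2 and the symptom level at the event correlate 0.8 with each other. A woman is dismissed if her event level is in the top fraction q and she is noticed, so expected dismissals per arm are 30 × q × detection. The analysis is a likelihood model with group-by-time means and unstructured covariance. It uses the same observed scores as the planned imputation and stands in for it. There are 30 women per arm and 5,000 runs (2,000 for equal detection). Dismissal is before T1 unless stated.

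| Affected (q) | Detection, TACAD v control | Dismissed, TACAD v control | Bias toward TACAD (SD) | Significant in TACAD's favour (nominal 2.5%) |
|---|---|---|---|---|
| 10% | 80% v 20% | 2.4 v 0.6 | 0.07 | 4.2% |
| 20% | 80% v 20% | 4.8 v 1.2 | 0.12 | 6.4% |
| 30% | 80% v 20% | 7.2 v 1.8 | 0.17 | 8.8% |
| 20% | 100% v 0% | 6.0 v 0 | 0.20 | 10.7% |
| 20%, baseline correlation 0.7 | 80% v 20% | 4.8 v 1.2 | 0.07 | 5.1% |
| 20%, dismissal after T1 | 80% v 20% | 4.8 v 1.2 | 0.03 | 3.3% |
| 20% | 50% v 50% | 3.0 v 3.0 | 0.00 | not tabulated |
| 20%, follow-up kept | 80% v 20% | none | 0.00 | 2.5% |

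**Milder and different triggers, large samples, same model.**
- 30% affected at 80% v 20% gives 0.18 SD, so the table's sizes do not depend on the small sample.
- 5% affected gives 0.04 SD at 80% v 20% and 0.01 SD at 60% v 40%.
- Lowering the correlation between event level and symptom score from 0.8 to 0.6, with 20% affected at 80% v 20%, lowers the bias from 0.13 to 0.08 SD.
- If the recorded T0 or T1 score is itself the trigger (20% affected, 80% v 20%), the bias after imputation is 0.00 SD.

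**What imputation achieves.** A second simulation let dismissal occur in either period, with 5 to 20% affected per period, detection 50 to 90% v 0 to 10%, within-person correlation 0.5 or 0.7, and state-to-score correlation 0.6 or 0.8. The complete-data difference at 3 months was biased by 0.04 to 0.36 SD toward TACAD. Imputation from observed scores left 0.02 to 0.21 SD, removing about one third (correlation 0.5) to about 60% (correlation 0.7). The complete-data analysis errs in the same direction and by more, so it cannot serve as the check on the imputed result.

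**With a true benefit of 0.5 SD.** Fewer TACAD women cross the threshold, which offsets unequal detection. In the first model the bias is 0.05 SD toward TACAD at 80% v 20%, 0.01 SD toward TACAD at 60% v 30%, and 0.04 SD against TACAD at equal detection. The second gives 0.02 to 0.11 SD toward TACAD at 5:1 to 9:1 detection, 0.00 to 0.03 SD toward TACAD at 2:1, and 0.03 to 0.09 SD against TACAD at equal detection.

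**The case against.** The case on the other side has real force.

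- **Detection by arm is inferred.** Section 32 also describes detailed screening questions at entry, both arms fill in the same symptom instruments, and all online interactions are monitored. A reader might infer that control women cannot be noticed. The documents do not support that: they show fewer channels in the control arm, not none. What stands is that the nurse chats and the TACAD social media site are extra channels.
- **The trigger may be recorded.** If a questionnaire answer prompts the PHQ-9, imputation from that score can handle the loss. The plan does not say what prompts it, so this limits the concern without answering it.
- **The inputs may be generous.** Only women with severe signs are screened, so many with moderate scores would never be tested, and the symptom index also covers physical complaints. This favours the lower part of the range.
- **The study is a small, exploratory pilot.** The 95% half-width is 1.96 × √(2/30) = 0.51 SD unadjusted, or 0.51 × √(1 − 0.5²) = 0.44 SD after adjusting for a baseline correlated 0.5. The bias lies inside that noise. But it is systematic, and Aim 2 still tests hypotheses.
- **Dismissal is a safety rule.** Changing it needs clinical and IRB judgement. The safety purpose is served by the referral and emergency steps; the documents give no reason why questionnaires must also stop.

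A reader might also infer that dismissed women's existing data are deleted, because Sections 5 and 38 remove the data of women who withdraw. The text does not say that dismissal counts as withdrawal, so this is an ambiguity to settle, not a finding.

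**Conclusion.** The concern holds in conditional form. The documents establish that the rule stops collection of a primary outcome for women selected by their symptoms, that nothing keeps them in follow-up despite the declared intent-to-treat analysis, and that staff contact is greater in the TACAD arm.

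They do not establish that the comparison is tilted toward TACAD, or that imputation fails outright. With no true effect, more detection in TACAD and distress arising between questionnaires, the bias left after imputation is about 0.01 to 0.2 SD toward TACAD. It is about zero with equal detection or a recorded trigger. With a true 0.5 SD benefit it runs from small toward TACAD to small against it. Every size rests on assumed event rates, detection rates and correlations.

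The change is worth making because it avoids avoidable symptom-dependent loss in all these cases, and because scores not collected cannot be recovered later. One reference cited in Section 5 concerns selection and pattern-mixture models, but the section states no analysis that allows for worse unseen scores.

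**What to change.** **Phase 2 (Aim 2) and Section 32.** Keep the PHQ-9 referral and all emergency steps. Replace dismissal with stopping or pausing TACAD and AA website use if the consulting clinician advises it. Still invite the woman to the T1 and T2 questionnaires unless she declines or the clinician advises against it.

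**Section 5.** State that a PHQ-9 stop is not withdrawal, so data already given are kept and she is analysed in her randomised arm. Report the number of stops in each arm beside the symptom result. For scores still missing after a stop, repeat the imputation with those women's symptom scores made worse, for example by 0.5 and 1.0 SD, labelled as assumed values. In the first simulation, unseen T2 scores of dismissed TACAD women were 0.91 to 1.11 SD worse than imputed at baseline correlation 0.5, and 0.57 to 0.67 SD worse at 0.7.

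**Cost.** An IRB modification, a consent-form change, a few lines in Section 5, and up to two further $50 gift certificates (2 × $50 = $100) per affected woman. Some women will decline, so the zero bias under full follow-up is a best case. Outcomes will also include any effect of psychiatric referral, which may be more frequent in TACAD and should be stated when results are reported.
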